9.2. Sample Size Determination

*Intra subject variability of 21% was chosen as clinically meaningful estimate based on the Sensitivity analysis on the variability estimates of 17% performed using 95th percentile approach.⁸

A sample size of 27 participants (adjusted for 9 subjects per sequence) without dropouts will be appropriate to provide 90% power for 90% confidence interval for the ratio of

Test to Reference for log-transformed C_{max} and AUC to lie within the acceptance region of bioequivalence 80% to 125%. This estimate is based on the ratio of Test product and Reference product is 0.95 and intra subject variability of 21% of Griseofulvin.

A sample size of 36 subjects are proposed for this 3-way cross-over study considering the dropouts and withdrawal of participants.

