The whole study will be divided into three periods. For each period, eligible participants will be randomized to either T1T2R, T2RT1 or RT1T2 treatment sequence according to 1:1:1 ratio.

Disclosure Statement: This is an open label study with 3 periods and only the bio-analytical investigator will be blinded to the treatments administered to the subjects.

Number of Participants:

A maximum of 36 participants will be randomly enrolled to study treatment such that approximately 27 evaluable participants complete the study.

Treatment Groups and Duration:

[figure not shown]
Excluding screening period, the duration of clinical phase will be approximately 20 days from Day-1 to Day 19 including a washout period of at least 7 days (not more than 14 days) for each study period.

The participants will be housed from at least 10.50 hrs before dosing until 24.00 hrs post dose in the centre for each study period. Activities beyond 24.00 hrs will be conducted on ambulatory basis.

In each period, single oral dose [Test Product (T1): 1 x 500 mg Tablet or Test Product (T2): 1 x 250 mg Tablet or Reference Product (R): 1 x 500 mg Tablet] of the study treatments will be administered to the participants as per randomization with 240 ± 2 mL of water at ambient temperature under fed condition.

Data Monitoring or Other Committee: No

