3. OBJECTIVES AND ENDPOINTS

Objectives	Endpoints
Primary	Primary

 To determine whether the Test Product (T1): Griseofulvin Tablets, 500 mg is bioequivalent to Reference Product (R): Griseofulvin Tablets, 500 mg (Grisovin) in healthy participants. To evaluate the dose proportionality across the dose range of 250 mg to 500 mg after single dose administration of Test Product (T2): Griseofulvin Tablets, 250 mg and Test Product (T1): Griseofulvin Tablets, 500 mg in healthy participants. 	
 C_{max}, AUC_{0-t} and AUC_{0-inf} for griseofulvin AUC_{0-t} and C_{max}
Secondary	Secondary

 To monitor the safety and tolerability of a single oral dose of Test Product (T1): Griseofulvin Tablets, 500 mg; Test Product (T2): Griseofulvin Tablets, 250 mg and Reference Product (R): Griseofulvin Tablets, 500 mg (Grisovin). 	
 Safety and tolerability as measured by adverse events, vital signs and clinical laboratory measurements.

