If the 90% confidence interval of geometric mean ratio of C_{\max} , AUC_{0-t} and AUC_{0-inf} between test (T1) and reference (R) products falls within the range of 80.00% to 125.00% for Griseofulvin, the null hypothesis will be rejected. In this case the test product (T1) will be concluded as bioequivalent to the reference product R.

If bioequivalence is demonstrated between the Test product (T1) and reference product (R), the following step II will be followed.

Step 2: For dose proportionality (T2 vs. T1):

Dose normalization will be done for test product T2 for AUC_{0-t} and C_{\max} parameter by multiplying with the correction factor 2.

PROC MIXED procedure will be used for analysis of variance and the estimation of least square mean differences (Test (T2) - Test (T1)) of the test (T2) and test (T1) products on the log-transformed pharmacokinetic parameter AUC_{0-t} and C_{\max} . The corresponding standard errors of the differences will also be computed. Based on these parameters, the 90% confidence intervals will be constructed for the least square mean differences of log-transformed parameter AUC_{0-t} and C_{\max} . The antilog (or exponential) of the limits obtained from the log-transformed data will give the 90% confidence interval for the ratio of geometric means of test (T2) and test (T1) products.

Null hypothesis will be rejected if the 90% confidence interval of geometric mean ratio of AUC_{0-t} and C_{\max} between test (T2) and test (T1) products falls within the range of 80.00% to 125.00% for Griseofulvin.

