9.4. Statistical Analyses

The statistical analysis plan will be finalized prior to study initiation and it will include a more technical and detailed description of the statistical analyses described in this section. This section is a summary of the planned statistical analyses of the most important endpoints including primary and key secondary endpoints.

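### The 90% power in Protocol 9.2 is for one parameter of T1 vs R, not for the three-parameter BE rule (about 80–87% at 27 evaluable), and the texts disagree on whether T2/T1 intervals depend on Step 1

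*Protocol*

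**What the plan says.** Protocol 9.2 gives one calculation: "A sample size of 27 participants (adjusted for 9 subjects per sequence) without dropouts will be appropriate to provide 90% power". The target is log-transformed Cmax and AUC; the text does not say whether the power is for each parameter or for all together. On inputs: "This estimate is based on the ratio of Test product and Reference product is 0.95 and intra subject variability of 21% of Griseofulvin". The 21% was raised from a base estimate of 17%. The Synopsis sets the working target: "A maximum of 36 participants will be randomly enrolled to study treatment such that approximately 27 evaluable participants complete the study".

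The decision rule for T1 vs R (Protocol 9.1 and 9.4.3, SAP 8.1.4.1) needs the 90% intervals for Cmax, AUC0-t and AUC0-inf all to lie within 80.00–125.00%.

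Dose proportionality of T2 vs T1 is the second primary objective (Protocol 3), judged on AUC0-t and Cmax. Protocol 9.1 and SAP 2.4 both say: "If bioequivalence is demonstrated between the Test product (T1) and reference product (R), the following step II will be followed". Step 2 then opens with "Dose normalization will be done for test product T2" and contains the T2/T1 model and its intervals. Earlier in the same two sections, under the T2 vs T1 hypotheses, 90% intervals are promised with no such condition. Protocol 9.4.2 likewise describes intervals for both contrasts without it. No section says what is reported if Step 1 fails.

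**The concern.** A reader of 9.2 will take 90% as the chance that the trial concludes bioequivalence, and will take the step from 36 to 27 as nine affordable losses. If the 90% belongs to one parameter while the claim needs three, both readings are too favourable.

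The gate raises a second matter. T2 vs T1 is the only planned comparison for the 250 mg tablet, because no 250 mg reference product is available (Protocol 1.1 and 2.2). If Step 1 fails, an analyst following the gate would not compute the T2/T1 ratio or interval, although the T2 data had been collected. An analyst following 9.4.2 would compute them. That choice should not be made after the T1/R result is known.

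**Working it through.** **Inputs from the plan.** TOST shown as a 90% interval; limits 0.80–1.25; T1/R ratio 0.95; CV 21%; 27 evaluable; 3×3 crossover. The model has sequence, period and treatment fixed and participant within sequence random (Protocol 9.4.1). Residual df is 2n − 4 = 50 if all three treatments are in the model. It is n − 2 = 25 if only T1 and R data are used; counting all three periods gives n − 3 = 24.

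**Reproducing the 90%.**
- σ = √ln(1 + 0.21²) = 0.2077; SE = 0.2077 × √(2/27) = 0.0565.
- Lower limit: (ln 0.95 − ln 0.80)/SE = 0.1719/0.0565 = 3.04. Subtracting t(0.95; 50) = 1.676 leaves 1.36, so Φ ≈ 0.91. The upper limit adds almost no failures.
- Integrating over the chi-square distribution of the residual variance: 91.1% (df 50) or 90.4% (df 25).
- Normal approximation: n = 2 × 0.2077² × (1.645 + 1.282)² / 0.1719² ≈ 25.0, which rounded up to a multiple of 3 is 27.
- 27/0.75 = 36 matches the planned enrolment.

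So 27 and 90% are correct for one parameter.

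**Joint power for all three parameters.** The documents give no between-parameter correlation. Assumed: the same ratio and CV for each parameter, AUC0-t/AUC0-inf correlation 0.98, and Cmax–AUC correlation from 0 to 0.9; near perfect means 0.999 throughout. Every counted participant is taken to have all three periods. Three correlated log-differences and their residual variances were simulated with at least 100,000 trials per cell; repeat runs differ by a few tenths of a point.

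| Evaluable (df) | r = 0 | r = 0.5 | r = 0.9 | near perfect |
|---|---|---|---|---|
| 27 (25) | 80.6% | 82.7% | 86.4% | 89.9% |
| 27 (50) | 82.0% | 84.0% | 87.3% | 90.6% |
| 30 (56) | 86.7% | 87.8% | 90.6% | 93.1% |
| 33 (62) | 90.2% | 91.0% | 93.0% | 95.0% |
| 36 (34) | 92.2% | 92.9% | 94.6% | 96.2% |
| 36 (68) | 92.7% | 93.3% | 95.0% | 96.5% |

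With df 24 at n = 27 the r = 0 figure is 80.4%. As a hand check, if the two AUCs behave as one parameter independent of Cmax, 0.911² = 0.83, close to the 82.0% above.

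**Other cases at n = 27, df 50, r from 0 to 0.9.** CV 17% for all parameters: about 96–97%. CV 21% for Cmax only and 17% for AUC: about 89–91%.

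**Consequences.** At df 2n − 4, joint power reaches 90% at 30 to 33 evaluable participants, which allows 36 − 33 = 3 to 36 − 30 = 6 losses rather than 9. Step 1 fails in about 100 − 87 = 13% to 100 − 80 = 20% of trials in the planning case.

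**Effect of the gate on false claims.** With both true ratios at 0.80, n = 27 and parameters fully correlated, the chance of any false claim is 5.0% if the dose-proportionality claim is gated on Step 1 and 10.0% if both claims are ungated. Reporting an interval without making a claim leaves the 5.0% unchanged.

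**The case against.** **There is no arithmetic error.** This stands. A reader might infer from the joint figures that 27 was miscalculated or that the trial is undersized. The documents do not support that: 27 reproduces, 9.2 never claims joint power, and 36 evaluable participants give at least 92% throughout the range examined.

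**The 80–87% stacks conservative inputs.** It uses the raised CV and the loss of 9 of 36 participants. That is fair, and the milder cases above show it. But these are the plan's own planning values, and the 90% was stated under the same ones.

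**The joint figure rests on outside assumptions.** It does. With one common correlation across all three parameters, power at n = 27 is 76% at 0, 80% at 0.5, 84% at 0.8 and 88% at 0.95. The lower values are unlikely because AUC0-inf contains AUC0-t. Any number put into 9.2 must carry its assumptions.

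**The gate may not suppress the intervals.** A reader might infer that the T2/T1 intervals are definitely not produced if Step 1 fails. The documents do not settle that. Protocol 9.1 and SAP 2.4 state only the positive branch, and the hypothesis text and 9.4.2 describe the intervals unconditionally. On the other side, 9.4 describes itself thus: "This section is a summary of the planned statistical analyses of the most important endpoints including primary and key secondary endpoints". Its silence on the gate may therefore be brevity. T2 parameters would in any case be summarised and listed (SAP 10.4.1 and 10.8.2); what is in doubt is the T2/T1 ratio and its interval.

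**The gate has a rationale.** It does: T2 is linked to the reference only through T1. That justifies gating the claim, not withholding the estimate.

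**Conclusion.** The point holds as one of labelling and reporting. The 90% in 9.2 is power for a single parameter of T1 vs R. Under the plan's CV, ratio and 27 evaluable participants, the chance of meeting the full bioequivalence rule is about 80–87%, and about 90–91% only if the parameters are almost perfectly correlated. The range depends on the correlations and df stated above. The planned 36 is adequate and need not change.

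On Step 2, the two documents carry an internal inconsistency: gated text beside unconditional text for the same intervals. Read by the gate, the estimate for a primary objective would not be produced if Step 1 fails.

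A reader might also infer that T2 vs T1 is underpowered because 9.2 gives it no ratio or power. The documents do not show this. At 27 evaluable and CV 21%, its two-parameter rule has about 83–88% power if the ratio is 0.95 and 95–96% if it is 1.00 (both ratios assumed; correlation 0 to 0.9), and SAP 10.8.4 lists a sample-size appendix that may say more. Stating the assumed ratio would be a useful clarification only.

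**What to change.** 1. In Protocol 9.2, keep N and restate the power, using the same assumptions at both sizes. For example: *With 27 evaluable participants, CV 21% and T1/R ratio 0.95, power is about 90–91% for each parameter of T1 vs R taken singly. Power to meet the limits on Cmax, AUC0-t and AUC0-inf together is about 80–87% with 27 evaluable participants and about 92–95% with 36. This assumes the same ratio and CV for all three parameters, a within-subject Cmax–AUC correlation of 0 to 0.9, an AUC0-t/AUC0-inf correlation of 0.98, and residual df between n − 2 and 2n − 4.*

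2. In Protocol 9.1 and SAP 2.4, at the Step 2 condition, and in line with the hypothesis text there and with 9.4.2, add: *The T2/T1 ratios with 90% confidence intervals for Cmax and AUC0-t will be computed and reported whatever the Step 1 result. Dose proportionality will be formally concluded only if Step 1 is met.* Make this change before the data are analysed.

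The cost is a less favourable stated power, a short simulation and a little more reporting. No participants, samples or acceptance limits change.

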9.3. Populations for Analyses

Three (3) populations sets are defined for analysis purposes.

Safety Analysis Set

The safety population will include all randomized participants who receive at least one dose of study medication. The safety population will be used for all analyses of safety data. Individual pharmacokinetic parameters and its descriptive statistics will be presented.

BE Analysis Set

The data of subjects completing at least 2 periods with 500mg test and 500mg reference treatments of the study will be subjected to statistical analysis.

Dose Proportionality Analysis Set

The data of subjects completing at least 2 periods with 500mg test and 250mg test treatments will be subjected to dose proportionality analysis.

The following populations are defined:

Population	Description
Enrolled	All participants who signed the ICF
Randomized	All participants assigned to study treatment.
BE Analysis Set	The data of subjects, completing at least 2 periods with 500mg test and 500mg reference treatments of the study will be subjected to statistical analysis.
Safety Analysis Set	The safety population will include all randomized participants who receive at least one dose of study medication. The safety population will be used for all analyses of safety data. Individual pharmacokinetic parameters and its descriptive statistics will be presented
Dose Proportionality	The data of subjects completing at least 2 periods with 500mg

Analysis Set	test and 250mg test treatments will be subjected to dose proportionality analysis
--------------	---

9.4. Statistical Analyses

The statistical analysis plan will be finalized prior to study initiation and it will include a more technical and detailed description of the statistical analyses described in this section. This section is a summary of the planned statistical analyses of the most important endpoints including primary and key secondary endpoints.

9.4.1. Analysis of Variance

Step 1: For BE Demonstration (T1 vs. R):

ANOVA will be performed using PROC MIXED on log-transformed pharmacokinetics parameters C_{\max} , AUC_{0-t} and AUC_{0-inf} at α level of 0.05.

The analysis of variance model will include sequences, period and treatment as fixed factors and participants nested within sequence as random factor [i.e. Model LC_{\max} or $LAUC_{0-t}$ or $LAUC_{0-inf}$ = sequence period treatment (fixed factors) and random: Participant (Sequence) (random factor)].

A separate ANOVA model will be used to analyze each of the parameters. All main effects will be tested against the residual error (mean square error) from the ANOVA model as the error term.

Each analysis of variance will also include calculation of least-square means, adjusted differences between formulation means and the standard error associated with these differences.

Step 2: For dose proportionality (T2 vs. T1):

ANOVA will be performed using PROC MIXED on log-transformed pharmacokinetics parameter AUC_{0-t} and C_{\max} at the α level of 0.05.

The analysis of variance model will include sequences, period and treatment as fixed factors and participants nested within sequence as random factor [i.e. Model $LAUC_{0-t}$ or LC_{\max} = sequence period treatment (fixed factors) and random: Participant (Sequence) (random factor)].

A separate ANOVA model will be used to analyze each of the parameters. All main effects will be tested against the residual error (mean square error) from the ANOVA model as the error term.

Each analysis of variance will also include calculation of least-square means, adjusted differences between formulation means and the standard error associated with these differences.

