A validated LC-MS/MS analytical methodology will be used for the determination of Griseofulvin from the human plasma samples. Validation of the methodology will be carried out in accordance with applicable guidelines and the applicable SOP of analytical facility of Accutest Research Laboratories (I) Pvt. Ltd which are designed in accordance with the regulatory guidelines such as USFDA, EMEA, DCGI etc.

The following parameters (as applicable for BE demonstration and for dose proportionality) will be calculated for each participant-formulation combination using the non-compartmental model by using statistical package SAS[®] 9.2 or higher version:

All concentration values below the limit of quantification (BLQ) will be set to zero for the estimation of pharmacokinetic parameters.

If the pre-dose value is >5 percent of C_{max} , the respective period of that subject will be dropped from all PK evaluations and statistical evaluations

The pharmacokinetic samples of subjects dropped out or withdrawn due to vomiting / diarrhoea or any other reason will not be analyzed for the respective study period. The samples of subjects completing at least 2 periods of the study will be subjected to statistical analysis.

Depending upon availability of data, the subject will be either included in bioequivalence evaluation or dose proportionality evaluation.

Primary parameters

C_{max}	Maximum observed drug concentration during the study.
AUC_{0-t}	Area under the plasma concentration - time curve measured to the last quantifiable concentration, using the linear trapezoidal rule.
AUC_{0-inf}	AUC_{0-t} plus additional area extrapolated to infinity, calculated using the formula $AUC_{0-t} + C_t/K_{el}$, where C_t is the last measurable drug concentration and K_{el} is the elimination rate constant.

Secondary parameters

T_{max}	Time to observe maximum drug concentration. If the maximum value occurs at more than 1 time point, T_{max} is defined as the first time point with this value.
AUC_{0-t} / AUC_{0-inf}	Ratio of AUC_{0-t} and AUC_{0-inf}
Residual area	Extrapolated area $(AUC_{0-inf} - AUC_{0-t}) / AUC_{0-inf}$

K_{el}	Apparent first – order terminal elimination rate constant calculated from a semi-log plot of the plasma concentration versus time curve, using the method of least square regression.
$t_{1/2}$	Terminal half-life as determined by quotient $0.693/K_{el}$

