9.4.3. Acceptance Criteria for Bioequivalence

Bioequivalence will be concluded if:

The 90% confidence interval of geometric mean ratio of log-transformed C_{max} , AUC_{0-t} and AUC_{0-inf} between test (T1) and reference (R) products fall within the range of 80.00% to 125.00% for Griseofulvin.

Dose proportionality will be concluded if:

The 90% confidence interval of geometric mean ratio of log-transformed AUC_{0-t} and C_{max} between test (T2) and test (T1) products falls within the range of 80.00% to 125.00% for Griseofulvin.

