8.1.4.1. Statistical Methodology Specification

The following pharmacokinetic statistical analyses will only be performed if sufficient data is available (i.e. if participants have well defined plasma profiles).

Endpoint / Variables
Primary end points for BE Demonstration (T1 vs. R): C _{max} , AUC _{0-t} and AUC _{0-inf} Primary end points for dose proportionality (T2 vs. T1) :C _{max} , AUC _{0-t}
Model Specification
ANOVA will be performed on Log-transformed C _{max} , AUC _{0-t} and AUC _{0-inf} using Proc Mixed Model. Model LC _{max} or LAUC _{0-t} or LAUC _{0-inf} = sequence period treatment (fixed factors) and random: Participant (Sequence) (random factor)]
Model Checking & Diagnostics
A separate ANOVA model will be used to analyze each of the parameters. All main effects will be tested against the residual error (mean square error) from the ANOVA model as the error term. Each analysis of variance will also include calculation of least-square means, adjusted differences between formulation means and the standard error associated with these differences. 
 • For the Proc Mixed Model, model assumptions will be checked, and appropriate adjustments may be applied based on the data. • Distributional assumptions underlying the model used for analysis will be examined by obtaining a normal probability plot of the residuals and a plot of the residuals versus the fitted values (i.e. checking the normality assumption and constant variance assumption of the model respectively) to gain confidence that the model assumptions are reasonable. • Non-parametric analyses will be conducted on un-transformed parameter T_{max}.
Model Results Presentation
Bioequivalence will be concluded if: The 90% confidence interval of geometric mean ratio of log-transformed C _{max} , AUC _{0-t} and AUC _{0-inf} between test (T1) and reference (R) products fall within the range of 80.00% to

125.00% for Griseofulvin.

Dose proportionality will be concluded if:

The 90% confidence interval of geometric mean ratio of log-transformed AUC_{0-t} and C_{max} between test (T2) and test (T1) products falls within the range of 80.00% to 125.00% for Griseofulvin.

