10.4. Appendix 4: Derived and Transformed Data

10.4.1. Pharmacokinetic

PK

• Plasma sample analysis will be carried out by Accutest Research Laboratories (I) Pvt Ltd. Griseofulvin plasma concentrations will be determined using the currently validated methodology. The actual sampling times, will be used in the PK calculations.• Griseofulvin plasma concentration-time data will be analyzed by non-compartmental methods with SAS software version 9.4 and derived PK parameters will be summarized and listed. Derived Pharmacokinetic parameters will be summarized by treatment group. Mean, Median, Min, Max, SD for untransformed pharmacokinetic parameters• For log-transformed data, geometric mean, 90% CI of geometric mean, T/R ratio (%), mean square error (mse), , intra-subject variability, power of log-transformed data will be reported.• Graphical summary for mean data will be presented using nominal sampling times. Graphical summaries for individual subjects will be presented using actual sampling times.

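### Does testing every main effect against the residual error, sequence included, undermine the crossover analysis?

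*Protocol*

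**What the plan says.** Protocol section 9.4.1 describes an analysis of variance run in PROC MIXED on log-transformed parameters. Sequence, period and treatment are fixed, with "participants nested within sequence as random factor". It then adds, once for the T1 versus R step and once for the T2 versus T1 step: "All main effects will be tested against the residual error (mean square error) from the ANOVA model as the error term".

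SAP section 8.1.4.1 gives the same model under its model-specification heading ("random: Participant (Sequence) (random factor") and repeats the error-term sentence under model checking and diagnostics. Protocol section 9.4 says of the SAP that "it will include a more technical and detailed description of the statistical analyses described in this section", but on this point the SAP adds nothing, and SAP section 2.1 declares no changes.

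The decision rule is in protocol section 9.4.3. For each comparison it is "The 90% confidence interval of geometric mean ratio of log-transformed" parameters that must fall within 80.00% to 125.00%. SAP section 10.4.1 lists what is reported on the log scale, starting "For log-transformed data, geometric mean, 90% CI of geometric mean, T/R ratio (%), mean square error (mse" and continuing with intra-subject variability and power. No sequence test is in that list.

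**The concern.** Each participant receives one sequence, so differences between sequences are differences between groups of people. The residual in a crossover measures variation within people. Judging a between-person effect against within-person noise gives a p-value that is too small whenever people differ from one another at all.

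The sentence makes no exception for sequence, which is a listed fixed factor. It also conflicts with declaring participants random in the same section. A programmer who followed it literally could report a significant sequence effect that is not there, and a reader could take that as a sign of carry-over or faulty randomisation.

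**Working it through.** **1. The plan's own figure.** Protocol section 9.2 gives 27 participants, 90% power, true ratio 0.95, intra-subject CV 21% and limits 80% to 125%. The within-participant log variance is ln(1 + 0.21²) = 0.0432, and the standard error of a treatment difference is √(2 × 0.0432 / 27) = 0.0565. Exact power for two one-sided tests is 0.911 with 50 residual degrees of freedom (three treatments in the model), or 0.903 with 24 (two treatments, three sequences). The figure reproduces. It depends only on the treatment contrast and the residual variance, and no sequence test enters it.

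**2. The specified fit.** Null trials were simulated with 9 participants per sequence and within-participant CV 21%. The model was a REML mixed model with random participant(sequence), and sequence was tested on 2 and 24 degrees of freedom. The documents give no between-participant CV for Cmax or AUC, so 10% to 50% was assumed. The rejection rate of the nominal 5% sequence test, over 20,000 trials per cell, was:

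| Data in model | Rejection rate |
|---|---|
| T1, T2 and R | 0.046 to 0.054 |
| T1 and R | 0.043 to 0.052 |
| T1 and T2 | 0.045 to 0.049 |

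The planned fit therefore tests sequence at about its nominal level.

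**3. The literal reading.** If the sequence mean square is divided by the residual mean square, its expectation is too large by the factor λ = 1 + c·σ²b/σ²w. Here c = 3 with three treatments, and c = 1.5 with two treatments, where sequence and period are not orthogonal. The true size is P(F(2, df) > F₀.₉₅(2, df)/λ).

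Worked case, with assumed between-participant CV 21% and three treatments: λ = 1 + 3 × 0.0432/0.0432 = 4. The critical value 3.183 falls to 3.183/4 = 0.796, and the size is 0.457.

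| Assumed between-participant CV | Three treatments (df 50) | Two treatments (df 24) |
|---|---|---|
| 0% | 0.050 | 0.050 |
| 10% | 0.163 | 0.101 |
| 21% | 0.457 | 0.275 |
| 30% | 0.637 | 0.439 |
| 40% | 0.756 | 0.583 |
| 50% | 0.825 | 0.682 |

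These rates belong to a ratio the plan does not call for. They are not properties of the planned analysis.

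**4. Effect on the primary contrasts.** In 1,500 simulated complete trials, treatment estimates and standard errors from the mixed model were compared with those from an analysis using only the within-participant residual. The standard errors differed by less than 1e-7 and the estimates by less than 1e-15.

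**5. Missing periods.** Protocol section 8.5 says: "The samples of subjects completing at least 2 periods of the study will be subjected to statistical analysis". It is fair to ask whether the residual is still the right error term for treatment when a period is absent. Protocol section 9.3 settles this for the primary comparisons. The bioequivalence set takes "The data of subjects completing at least 2 periods with 500mg test and 500mg reference treatments", and the dose-proportionality set likewise requires both test strengths. A participant in either set can therefore lack only the third treatment.

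In a three-treatment model with n = 27, take the variance of the contrast from within-participant information alone and divide it by its mixed-model variance. For T1−R with T2 missing, and for T2−T1 with R missing, the ratio is 1.000 with 3, 6 or 9 participants incomplete, spread equally over sequences. The residual remains the right error term for treatment in both sets.

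**The case for a change.** The strongest case for amending is that a plan should not name one procedure and then describe another error term. The protocol promises that the SAP will be more technical, yet the SAP repeats the inaccurate sentence. Residual mean square is a listed output and the SAS output is appended to the report, so someone could form the literal ratio. Neither document states a denominator degrees-of-freedom method, and correcting one sentence in three places costs almost nothing.

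It stands that the sentence is inaccurate for sequence and inconsistent with the random term. The route to harm does not stand. The appended output would come from PROC MIXED with participant(sequence) random, and so would carry a sequence test of about the right size. The wrong p-value needs an extra hand calculation that neither document describes. Even then it would feed no hypothesis, acceptance criterion, listed log-scale output or carry-over rule.

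**Conclusion.** The sentence is a clerical slip: accurate for period and treatment in complete data, inaccurate for sequence. An analyst who runs the specified model gets the right sequence test without noticing the conflict. Amending the plan would change no contrast, interval, decision or sample size, so no change is called for. If the text is edited for other reasons, it could say that the sequence test comes from the fitted mixed model.

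This rests on the specified PROC MIXED fit being run with participant(sequence) random and its default degrees of freedom. With two treatments the sequence test is approximate, but its simulated size is still 4.3% to 5.2%. The inflation under the literal reading (16% to 82% with three treatments, 10% to 68% with two) depends on an assumed between-participant CV of 10% to 50% and on a calculation the plan does not contain.
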